EEG outcome measures analyses. We will conduct a repeated-measures ANCOVA with a within-subject factor of time (baseline and end-of-stimulation (EOS)), between-subject factor of intervention condition (active tDCS and sham) and covariates to test if there is a statistically significant difference in in the EEG outcome (Δtheta) across treatment groups. Pearson correlations will be used to examine beta PSD values in relation to craving scores. A separate ANCOVA with the same factors will be used to explore treatment group differences in resting state EEG beta PSD values. Covariates for both analyses will include the baseline measure of the evaluated outcome, as well as baseline variables found to vary significantly ($p < 0.05$) by intervention arm, or which significantly ($p < 0.05$) predict attrition at EOS. Post-hoc t-tests will be used to probe anticipated significant interactions.

5. Quality Assurance

All research personnel, will have formal training in research with human subjects (e.g., CITI training, NIH Human Subjects training). Drs. [name], [name], and [name] will provide training to and supervise research assistants. Research assistants will also have training in Good Clinical Practice.

Drs. [name] and [name] will be responsible for quality control of this study. They will review recruitment and retention reports, and AE reports on a weekly basis. The MPIs (or their designee) will inspect BL documents (consent forms, release of information) for completeness within a week after they are signed. The MPIs (or their designee) will also conduct protocol and data quality monitoring twice a year using a checklist. This monitoring will include reviewing other study records to ensure completeness.

6. Regulatory Issues

6.a, 6.c Reporting of SAEs, Non-Medication Trials

Drs. [name] and [name] will be responsible for overseeing the daily safety of all participants. There are several ways in which they will become aware of adverse events. First, research staff will ask participants about serious adverse events (as defined by Office of Human Research Protections (OHRP); e.g., inpatient hospitalization) at each research contact point (UG3: baseline, week 2 assessment, 5 tDCS appointments, 2 fMRI; UH3: baseline,

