week 2, 4, 6, 8, 12 assessments, 5 tDCS appointments, 3 FMRI). For monitoring expected adverse effects of tDCS, we use the SAFTEE at each session that includes changes in physical health status. Deaths are reported by significant others when we try to locate participants who missed appointments. Butler Hospital has a psychiatric emergency room available 24 hours a day. All research procedures will be supervised by Drs. [name] and [name] who will be on call 24-hours a day.

Second, all study staff will be trained in the OHRP definitions of adverse events that are also unanticipated problems; serious adverse events; or unanticipated problems that are not adverse events. All study staff are required to report any event that might meet one of these criteria to one of the PIs immediately both verbally and in writing. When necessary, a report of a serious adverse event will result in one of the PIs contacting the participant to further assess the event.

Drs. [name] and [name] will meet weekly with research assistants to review staff experiences with participants. Based on the sources of information detailed above as well as direct patient contact and/or consultation with the scientific team, Drs. [name] and [name] will determine if the event is: a) a serious adverse event that is also an unanticipated problem; b) an unanticipated problem that is not an adverse event. The Butler Hospital IRB require that fatalities related to the study be reported within 24 hours, all other serious adverse events related to the study be reported within 5 business/7 calendar days, and other serious adverse events related to the study be reported at the continuing review (at least annually).

6.d Reporting of IRB Actions to NIDA

All SAEs will be reported to NIDA within 72 hours of the MPIs becoming aware.

6.e Report of changes of amendments to the protocol

Changes to the proposal must be approved by NIDA prior to implementation

6.f Trial stopping rules

This study will be stopped prior to its completion if: (1) the intervention is associated with adverse effects that call into question the safety of the intervention; (2) any new information becomes available during the trial that necessitates stopping the trial; or

6.g Disclosure of Conflict of Interest

[name]: None

[name]: None

[name]: None

[name]: None

7. Trial Safety

7.a Potential Risks and Benefits for Participants

Potential Coercion.

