Risks. It is possible that individuals may feel coerced into participating.

Minimization. Issues related to coercion can arise from the payments that participants can earn from assessment participation. The payments made amount to approximately \$20 per hour as compensation for assessment and travel time. This rate is consistent with local standards for research.

Risks due to tDCS.

Risks. There is some inherent risk with application of tDCS, mainly risk of skin irritation and, as in a small number of case reports, local skin burns where the electrodes are placed. Such cases have typically been seen only after repeated daily stimulation to the same region (Palm et al., 2008), or after unintentional abrasion of the skin with alcohol swabs prior to

stimulation (Loo et al., 2011). Though a possible risk, skin burns are rare. In a recent review of clinical research with tDCS, Brunoni and colleagues (2012) noted that “tDCS has been tested in thousands of subjects world-wide with no evidence of toxic effects to date.” The most common side effects include mild local sensations at the electrode sites, including tingling or itching, and moderate fatigue, and headache. In research experience totaling 567 tDCS sessions, Poreisz and colleagues (2007) reported that no participants requested tDCS be stopped or required any medical intervention during or after stimulation. Notably, adverse effects did not differ between healthy individuals and patients. Safety testing of tDCS has found high tolerability and no reports of discomfort by participants when stimulating for 20 minutes at either 1 or 2mA for 20 minutes (Iyer et al., 2005). There have also been a small number of case reports of hypomania induction during tDCS for depression interventions, in both individuals with bipolar and unipolar depression (Arul-Anandam, Loo, Mitchell, 2010; Galvez et al., 2011; Baccaro et al., 2010). Most recently, Brunoni, et al (2013) reported during a factorial design testing tDCS and the antidepressant sertraline, 7 of 120 participants developed mania or hypomania, with 5 of the 7 cases occurring in the combined tDCS+sertraline group. As the participants in that study were all drug-free prior to study entry, it is unknown whether this was due to starting an antidepressant medication, tDCS, or the combination.

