Minimization. To minimize risks due to tDCS, all participants will be carefully screened prior to tDCS for contraindications to tDCS. Those with a history of mood symptoms suggesting risk for hypomania or bipolar disorder will be excluded. Use of an electrically isolated power source (i.e., battery-powered DC stimulation device) also protects against delivery of more intense currents than intended. Participants with lesions or open wounds on the scalp will be excluded. Participants will be closely observed for signs of skin burns, discomfort, or other stress. During stimulation sessions, participants will be closely monitored to ensure the electrode sponges stay moist with saline (to enhance conductivity) and in good contact with the scalp in order to help prevent burns. Participants will have the option of discontinuing the study at any time and will be explicitly instructed to inform the tDCS administrator immediately if they experience any discomfort. The tDCS administrator will inform the supervising physician about any participant who has significant discomfort or a skin lesion that emerges after tDCS delivery. A Butler Neuromodulation Research Facility covering physician is available during all procedures to evaluate any participant or research staff identifying a concern related to study procedures. If there is any doubt about the mental or physical status of an individual before or after testing, the supervising physician will evaluate the participant and make a recommendation for cancelling the research procedure and /or arranging follow-up care, as indicated. Telephone or in-person follow-up will be arranged as needed and will not be considered a protocol deviation. Any participant that has experienced adverse effects will be evaluated, treated as necessary, and withdrawn from the study if deemed necessary.

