In order to assess for and monitor presence and tolerability of adverse effects, we will use a modified version of a tDCS Side Effects Questionnaire informed by Brunoni and colleagues¹¹. This is a 10-item measure that assess such effects as headache, neck pain, scalp pain, skin redness, sleepiness, difficulty concentrating, and acute mood changes. The measure will be administered after each tDCS session. For each item, participants are asked to report how bothersome each symptom on the form has been with response options "None," "Mild," "Moderate," or "Severe." For any item rated "severe," or any item which appears to significantly increase in severity over the course of the session, the evaluator will notify the covering physician immediately and the covering physician will provide further evaluation as medically necessary. tDCS administrators are encouraged to contact the covering physician about any additional tDCS related concerns and this will not be considered a protocol deviation. Reported side-effects endorsed will be reviewed during weekly meetings of study staff. Follow-up or further evaluation will occur as necessary.

In addition, in order to monitor participant safety during the intervention period, we will also have participants complete self-report measures to assess for increased manic or hypomanic symptoms (from the Altman Self-Rating Mania Scale (ASRM)). The ASRM will be administered at baseline and prior to the first and last session of tDCS (sessions 1 and 5). Scores ≥ 6 will be considered clinically significant and will require evaluation by a study clinician. Further, we will assess significant changes in affect such as anxiety/activation/anergia/sedation from the PANAS scale at the baseline and week 2 follow-up assessment. Lastly, changes in frequency and dosage of any medication will be monitored at every participant contact time point. The study physician will monitor affective symptom changes and make determinations as to whether the participant should discontinue the intervention and receive additional mental health treatment.

Risks due to FMRI.

Risks. The primary FMRI contraindications are claustrophobia, metal implants, and pregnancy. Some individuals may experience discomfort from loud noises inside the scanner.

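### After the side effects form that closes session 5, no scheduled contact clearly asks about delayed or persistent skin, scalp or headache effects of tDCS

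*Combined protocol and SAP*

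**What the plan says.** Section 6.a is the plan's account of adverse event collection; section 7.b only refers back to it. It states that "research staff will ask participants about serious adverse events", giving inpatient hospitalization as its example, "at each research contact point (UG3: baseline, week 2 assessment, 5 tDCS appointments, 2 fMRI; UH3: baseline", and then, for UH3, "week 2, 4, 6, 8, 12 assessments, 5 tDCS appointments, 3 FMRI". The next sentence reads "For monitoring expected adverse effects of tDCS, we use the SAFTEE at each session that includes changes in physical health status".

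Section 7.a, on tDCS risks, adds the 10-item tDCS Side Effects Questionnaire, whose items include skin redness, pain in the scalp and headache. On timing: "The measure will be administered after each tDCS session". The same section schedules a mania self-rating (ASRM) at baseline and before sessions 1 and 5, the PANAS at baseline and week 2, and a check of medication changes at every contact.

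On the risk itself, section 7.a puts skin irritation first, with local burns known from a small number of case reports. Of the burns it says "Such cases have typically been seen only after repeated daily stimulation to the same region", or after the skin had been abraded beforehand, and it calls them rare. The tDCS administrator is to tell the supervising physician about "a skin lesion that emerges after tDCS delivery". Telephone or in-person follow-up is arranged when needed and is not scheduled.

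**The concern.** The regimen is five 20-minute sessions at the same two electrode sites, on consecutive days if possible. That is the setting to which the plan itself ties skin burns. An effect that develops hours or days after one of the first four sessions can be picked up when the participant returns for the next one. After session 5 there is no next session, and the questions specified for later contacts do not cover local effects.

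A small burn, lasting scalp soreness or a persistent headache would normally not be serious, so the serious-event question would not draw it out. What is at stake is the completeness of the adverse event summary table in section 9.c. The DSMB uses adverse event rates to judge whether the study matches its prior assumptions, and the first stopping criterion in section 6.f rests on adverse effects. No efficacy analysis is affected.

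**Working it through.** The plan states no figure on this point, and the question involves no sample size, error rate or effect size. The check is to list each safety measure, find its last scheduled use, and ask whether it covers local effects.

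| Measure | Section | Last scheduled use | Asks about skin, scalp or headache? |
|---|---|---|---|
| Serious event question | 6.a | All contacts, to week 2 or post-treatment scan (UG3) and week 12 (UH3) | Only if the event is serious |
| tDCS Side Effects Questionnaire | 7.a | Straight after session 5 | Yes |
| SAFTEE | 6.a | Each session, undefined | Physical health changes; items not listed |
| ASRM | 7.a | Before session 5 | No, a mania scale |
| PANAS | 7.a | Week 2 | No, affect |
| Medication changes | 7.a | Every contact | Only indirectly |

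Contacts listed in section 6.a that remain once session 5 is closed, taking week 2 to fall after session 5:

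- UG3: the week 2 assessment and the post-treatment fMRI.
- UH3: the assessments at weeks 2, 4, 6, 8 and 12, and the later fMRI scans.

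*If session means tDCS session.* None of these contacts has a scheduled question on local effects. What remains is the serious event question and the medication check at all of them, plus one PANAS at week 2.

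*If session means any research contact.* The SAFTEE would run at all of them and, to the extent that its physical health items cover skin and scalp, would close much of the gap.

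The first reading is likelier. The sentence is about expected tDCS effects, and the list just before it calls the other contacts assessments and appointments. The wording does not settle it, however, and section 7.a does not mention the SAFTEE.

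*Is week 2 after session 5?* Section 2 allows the five sessions to take up to 10 days. If week 2 (day 14) is counted from the first session, it falls at least 14 − 10 = 4 days after session 5. If it is counted from an earlier baseline visit, a gap of more than 4 days before the first session combined with the full 10-day allowance would put session 5 after week 2. The documents do not fix the starting point, so the order is likely but not certain.

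*Would another route collect the event?* Under section 6.a, staff must report serious adverse events, adverse events that are also unanticipated problems, and unanticipated problems that are not adverse events. A non-serious skin effect that the plan already lists as expected fits none of these clearly. The duty to pass on a lesion that emerges later lies with the tDCS administrator, who has no scheduled appointment with the participant after session 5.

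**The case against.** The strongest reply is that the plan observes more than a quick reading of section 6.a suggests. Several parts of it stand.

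- A reader might infer that outside the tDCS sessions staff ask only about serious events. That is wrong: the PANAS at week 2 and the medication check at every contact are both presented in section 7.a as safety monitoring.
- A reader might infer that session 5 goes unobserved. It does not. The questionnaire follows that session too, and participants are watched for skin burns. The gap is confined to effects that start or persist after the participant has left.
- A reader might infer that adverse event data end at session 5. They do not. Follow-up when needed, weekly review of reported side effects, investigators on call around the clock, and later in-person visits (including the repeat EEG in UG3) are real routes. They depend on someone raising or noticing the problem, however, and none of them asks about local effects.
- Session may have a wider meaning. Section 2.d uses it where the loss described is from movement artifact, and the cue-reactivity text in 7.a uses it for the scan. This reading cannot be excluded.
- A reader might infer that risk peaks after session 5, or estimate how many cases would be missed. The documents give no dose-response, no rate and no account of delayed-onset skin effects, and they call burns rare.

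These points narrow the claim. They do not supply a scheduled question about local effects after session 5.

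**Conclusion.** The point holds in limited form. As most naturally read, the plan's last scheduled question on skin, scalp and headache effects comes immediately after session 5, and delayed or persistent non-serious effects of that session then depend on spontaneous report. The count of later contacts with such a question is zero in both phases.

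This rests on two assumptions: that session in the SAFTEE sentence means a tDCS session, and that week 2 follows session 5. If the first fails, most of the gap closes and the remedy is to define the word. If the second fails for some participants, the gap for them begins at a later contact.

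The number of affected participants cannot be estimated from the documents. Nor do they support a claim about bias in a comparison of tolerability between arms, since section 9.c does not say that the adverse event table is split by arm. This is an inexpensive improvement to safety data collection, not a defect in the trial's primary inference.

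**What to change.** In sections 6.a and 7.a, state that the existing 10-item tDCS Side Effects Questionnaire is also given at the first existing assessment after session 5. That is week 2 in both phases, or the next scheduled contact if session 5 falls later. The wording should make the questions cover the time since the last tDCS session. Alternatively, use the SAFTEE for this purpose and define session to include the post-treatment assessments. Either way, define session in 6.a, and include the responses in the adverse event table of the DSM report (section 9.c).

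The cost is one more short form per participant at a visit already planned, with no new instrument, visit or staff and no change to stimulation. The reported adverse event rate may rise slightly because more is asked.

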The optimal frequency, duration and number of tDCS sessions to maximize effects on craving, or any other construct in this young field, remain obscure. We chose to deliver 5 sessions of tDCS because this number has been used in prior successful tDCS craving interventions and must be balanced against adherence concerns. While we are hopeful that participants will complete 5 consecutive days of tDCS, the interruption of weekends and the transition from the ADP setting (where the tDCS protocol will start) where days are structured, to the community setting, raises the possibility of missed tDCS sessions and therefore we will allow these 5 sessions to occur over 10 days if necessary, as has been described in prior studies, tracking both average number of sessions received and period of treatment for analyses. The sham tDCS condition is included in our design to separate the effects of ongoing opioid treatment from the effect of active tDCS on craving. We decided not to include a third no-tDCS arm, as this would omit any nonspecific treatment effects (match for attention, expectation) of entering a neurostimulation treatment protocol. This protocol will provide a basis for future studies of tDCS stimulation parameters (frequency, duration, number) that could optimize adherence and treatment effects of drug use outcomes.

In phase two (UH3), we will perform a larger RCT using the same treatment protocol in 100 opioid dependent participants who recently initiated buprenorphine or methadone. Participants will be randomized to receive five sessions of tDCS+CCN priming stimulation vs. sham tDCS+CCN priming. Phase two will address long-term (3-month) neurobehavioral outcomes, including opioid relapse, craving, and sustained fMRI changes during a paradigm that challenges networks associated with craving (CR) and cognitive control (CCN). During the 12 weeks of opioid maintenance treatment, we will examine our primary clinical outcome, relapse (opioid use on >4 days per month and having an opioid positive urine screen), as well as days of opioid use.

2.c Inclusion/Exclusion Criteria:

UG3/UH3 Inclusion Criteria: (a) current opioid dependence, (b) between 21-50 years of age, (c) recent initiation of buprenorphine or methadone (<30 days)

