1) CR: Two 2x2 mixed ANOVAs will be used to determine whether mean response to cues during CR decline across nodes of the craving network (VS, amygdala, VMPFC), including salience network (AI, ACC) and increases in the CCN (MFG, IPL). Significant pre-post main effects and group x treatment interactions are predicted in each. Those who received tDCS+CCN priming are expected to exhibit greater change. Follow up analyses of individual nodes within each network and whole-brain voxel-wise contrasts will be conducted to inform phase 2 analyses.

2) n-Back: Two 2x2 mixed ANOVAs will be used to determine whether mean response to the n-Back challenge increases across nodes of the CCN (MFG, IPL) and the salience network (ACC and AI). Significant pre-post main effects and group x treatment interactions are predicted in each. Those who received tDCS are expected to exhibit greater change. Follow up analyses of individual nodes within each network and whole-brain voxel-wise contrasts will be conducted to inform phase 2 analyses.

3) Resting state: Two 2x2 mixed ANOVAs will be used to determine whether mean network coherence (functional connectivity) decreases across nodes of the craving network (VS, amygdala, VMPFC), including the salience network (AI, ACC) and increases in the CCN (MFG, IPL). Significant pre-post main effects and group x treatment interactions are predicted

in each. Those who received tDCS are expected to exhibit greater change. Parallel exploratory analyses will be conducted to examine resting state functional connectivity of the salience network and DMN.

In the UH3, neuroimaging analyses will generally parallel those described for UG3. We will use a 2x3 ANOVA (three time points) to test the hypothesis that tDCS+CCN priming will be superior to sham tDCS+CCN priming on both subjective and fMRI measures of craving and cognitive control at the end of 5 sessions and at 3-months post tDCS. This same analytical method will be used to test the effect of intervention on days of drug use at the end of 5 sessions and at 3-months. We will use the Pearson χ^2 -test of independence to compare tDCS+CCN priming to sham tDCS+CCN priming on relapse at 3-months.

FMRI data analyses

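### UH3 craving and days of use are tested at two follow-up times only; the plan gives any week 4, 6 and 8 data no role in that test and states no rule for people who miss week 12

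*Combined protocol and SAP*

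**What the plan says.** Section 6.a, 6.c explains that "research staff will ask participants about serious adverse events" at each contact. For UH3 it gives baseline and then "week 2, 4, 6, 8, 12 assessments, 5 tDCS appointments, 3 FMRI". Assessments are listed apart from stimulation appointments and scans.

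Section 4.c sets the UH3 analysis: "We will use a 2x3 ANOVA (three time points) to test the hypothesis" of superiority on subjective craving and on "fMRI measures of craving and cognitive control at the end of 5 sessions and at 3-months post tDCS". The same method is applied to "days of drug use at the end of 5 sessions and at 3-months". Relapse at 3 months is compared by a Pearson chi-square test.

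Section 2.a, 2.b describes the outcomes over a longer window: "During the 12 weeks of opioid maintenance treatment, we will examine our primary clinical outcome, relapse". Relapse there combines a monthly count of use days with a positive urine screen, and days of use are examined as well.

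Section 2.d expects 20% attrition over the five sessions and the first two scans, leaving 80 of 100. It places the third scan at 4 weeks and expects a missed third scan to reflect treatment drop-out or relapse.

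**The concern.** Three time points suit imaging, because there are three scans. Subjective craving and days of use can be asked about at any assessment, and five follow-up assessments are scheduled. The planned test names two follow-up times, so the plan does not say what becomes of anything recorded at weeks 4, 6 and 8.

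Two things are at stake. First, a conventional repeated-measures ANOVA needs every time point. Someone seen through week 8 but not at week 12 would leave the analysis entirely, including the end-of-sessions comparison. If that loss follows relapse, as section 2.d expects for the third scan, those who remain are a selected group. Second, with no rule stated, the choice of visits can be made after the data are seen.

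**Working it through.** **Plan's own figure.** The documents give no power figure for craving or days of use, so there is none to reproduce. The only UH3 figure (0.80 for relapse of 15% versus 39%) concerns a different outcome and is not at issue here.

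**Count of visits.** Five follow-ups are scheduled (weeks 2, 4, 6, 8, 12) and two are tested, which leaves 5 - 2 = 3 (weeks 4, 6, 8). Two inferences are needed. Baseline is taken as the third time point. Week 2 is taken as the end-of-sessions visit, because "we will allow these 5 sessions to occur over 10 days if necessary".

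**Assumptions for the rest.** Craving and use are recorded at each assessment. There are 40 analysed per arm (80 split 1:1; the ratio is not stated). The outcome has SD 1 at each visit. The documents give no correlations, so ranges are shown. The percentage changes below do not depend on the number per arm.

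**Precision of an average over follow-up, equal correlations.** With correlation r between follow-ups and r0 with baseline, the baseline-adjusted variance of a k-visit mean is V(k) = (1 + (k-1)r)/k - r0².

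| r | r0 | V(2) | V(5) | Reduction |
|---|---|---|---|---|
| 0.5 | 0.4 | 0.75 - 0.16 = 0.59 | 0.60 - 0.16 = 0.44 | 25% |
| 0.5 | 0.5 | 0.75 - 0.25 = 0.50 | 0.60 - 0.25 = 0.35 | 30% |
| 0.7 | 0.4 | 0.85 - 0.16 = 0.69 | 0.76 - 0.16 = 0.60 | 13% |
| 0.7 | 0.5 | 0.85 - 0.25 = 0.60 | 0.76 - 0.25 = 0.51 | 15% |

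**The same contrast, correlations that decay with time.** Let the correlation between weeks s and t be q^(|s-t|/4), with baseline at week 0. The adjusted variance is w'Sw - (w'c)², where w holds equal weights, S is the follow-up correlation matrix and c the correlations with baseline.

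| q per 4 weeks | Weeks 2 and 12 | All five | Change |
|---|---|---|---|
| 0.5 | 0.415 | 0.431 | +4% |
| 0.7 | 0.357 | 0.385 | +8% |
| 0.85 | 0.243 | 0.256 | +5% |

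Pure decay allows no measurement error. If 20-40% of the variance is visit-specific noise (an assumption), five visits have 9-24% less variance than two. The gain thus depends on a correlation pattern that nobody has stated.

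**What weeks 4-8 tell us about a missing week 12.** Under pure decay only the latest visit matters. With week 2 the latest, the share of week-12 variance explained is (q^(10/4))² = q^5. With week 8 the latest, it is (q^(4/4))² = q².

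| q | Baseline and week 2 | Adding weeks 4-8 |
|---|---|---|
| 0.5 | 3% | 25% |
| 0.7 | 17% | 49% |
| 0.85 | 44% | 72% |

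Under equal correlations (baseline included) the share is kr²/(1 + (k-1)r) for k earlier measurements. Going from k = 2 to k = 5 raises it from 0.50/1.5 = 33% to 1.25/3 = 42% at r = 0.5, and from 0.98/1.7 = 58% to 2.45/3.8 = 64% at r = 0.7. The interim visits add information about week 12 in both patterns, and most in the pattern where averaging helps least.

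**How many people this affects.** The 20% in section 2.d falls in the sessions and first two scans. Later loss is not quantified. Each person seen at weeks 4-8 but not at week 12 is 1/80 = 1.25% of the planned analysed sample.

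**The case against.** A reader might infer that the three interim visits are wasted. The documents do not support that. The list sits in the safety section, so the visits have a stated safety purpose. Relapse is the primary clinical outcome and has a monthly criterion, so weeks 4 to 8 may well supply use-day counts and urine screens for it, and for days of use over 12 weeks. Week 4 also coincides with the third scan as timed in section 2.d. Nor does any section say that craving or use is recorded at weeks 4, 6 or 8. If it is not, nothing is being discarded, and using those visits means collecting more data. All of this stands, and it limits the point to the craving and days-of-use test.

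A second tempting reading is that the plan gives up a fixed amount of power. That also fails: the gain from averaging disappears under pure decay.

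A third objection is that an average over weeks 2 to 12 answers a different question from the planned one, which concerns two named times. That is right. With complete data and an unstructured covariance, the two planned contrasts gain essentially no precision from extra visits. The average should therefore not replace them.

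These objections leave the missing-data problem in place. No rule for missing UH3 craving or use data is given, and the named method conventionally needs complete cases.

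**Conclusion.** The concern holds in limited form. Weeks 4, 6 and 8 have no stated role in the craving and days-of-use test, and the plan does not say whether they feed relapse or the 12-week use count. The chief benefit of using them is to retain participants with partial follow-up and to lower the risk of bias from drop-out. Its size cannot be computed, because loss after the second scan is not given. A mixed model lowers that risk only so far as the recorded data explain who is lost; it does not remove bias from unrecorded relapse.

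For the supplementary average, the effect on variance ranges from 4-8% more (pure decay) to about 30% less (equal correlations 0.5-0.7, baseline correlation 0.4-0.5). This rests on the outcomes being recorded at every assessment. It is a cheap improvement to the plan and does not make the planned test invalid.

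**What to change.** In section 4.c:

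- Keep the three-time-point analysis for imaging. Reconcile the 4-week third scan in section 2.d with the 3-month imaging test in section 4.c.
- For subjective craving and days of use, fit one likelihood-based mixed model to all follow-up assessments at which they are recorded, with arm, visit, arm-by-visit and the baseline value.
- Keep the end-of-sessions and 3-month contrasts as the planned tests. Report the weeks 2-12 average only as a supplementary contrast.
- State at which visits craving and use are recorded, and which visits supply the cumulative use-day count and the relapse determination.

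The cost is wording and slightly more analysis work, with no added visits or participants. If craving or use is not now recorded at weeks 4, 6 and 8, brief ratings at those visits would be a small addition to data collection. The downside of the average is that it dilutes an effect present only early or only late, which is why the two time-specific contrasts stay.
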